#### **9.4.5 Electrocardiogram (ECG)**

ECGs will be performed for safety monitoring purposes only and will not be presented.

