**Statistical Analysis:**

For Part A, the area under the concentration versus time curve (AUC) from time zero to infinity ( $AUC[0-\infty]$ ), AUC from time zero to time  $t$ , where  $t$  is the last sample with a measurable concentration ( $AUC[0-t_{last}]$ ), and maximum observed drug concentration ( $C_{max}$ ) will be log-transformed and analyzed using a linear fixed-effects model. The model will include dosing regimen arm as a fixed effect. The dosing regimen differences between the Test 1 arm and the Reference arm will be back-transformed to present the ratios of geometric least squares (LS) means and the corresponding 90% confidence interval (CI).

The time to  $C_{max}$  ( $t_{max}$ ) of LY3074828 between the 2 x 1-mL PFS (Reference) and the 1 x 2-mL PFS (Test 1) will be analyzed using a Wilcoxon rank sum test for Part A. Estimates of the median difference, 90% CIs, and p-values from the Wilcoxon rank sum test will be calculated.

Additional PK analyses may be conducted for Part A if deemed appropriate.

In Part A, a linear fixed-effects model will be used to analyze the 0-hour (post-injection) pain VAS score and SF-MPQ total score. The model will include treatment (Reference or Test 1) as a fixed effect. The LS means and differences in LS means (between Test 1 and Reference) will be presented along with the corresponding 90% CI.

A similar model will be used to analyze the 0-hour (post-injection) pain VAS score and SF-MPQ total score in Part B.

The following comparisons will be performed in Part B:

- Test 2 versus Test 3 (slow versus fast injection for 2-mL AI)
- Test 4 versus Test 5 (slow versus fast injection for 1-mL AI)

For Parts A and B, safety parameters will be listed and summarized using standard descriptive statistics.

Additional safety and tolerability analyses will be performed if warranted upon review of the data.

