#### **10.3.1.2.4. *Statistical Evaluation of Other Safety Parameters***

Other safety parameters that will be assessed include clinical laboratory parameters, vital signs, and ECG parameters. The parameters, and changes from baseline (predose) where appropriate, will be listed and summarized using standard descriptive statistics. Additional analyses will be performed if warranted upon review of the data.

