**Table AMAQ.4. Amendment Summary for Protocol I6T-MC-AMAQ Amendment(b)**

Section # and Name	Description of Change	Brief Rationale
Section 10.3.7. Interim Analysis	An update has been made to introduce an exploratory interim analysis to this study.	An exploratory interim analysis is planned for this study.

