### **3. INTRODUCTION**

This SAP has been developed after review of the Clinical Study Protocol (final version dated 13 December 2017) and Protocol Amendment (a) (final version dated 12 March 2018).

This SAP describes the planned analysis of the safety, tolerability and pharmacokinetic (PK) data from this study. A detailed description of the planned TFLs to be presented in the clinical study report (CSR) is provided in the accompanying TFL shell document.

The intent of this document is to provide guidance for the statistical and PK analyses of data. In general, the analyses are based on information from the protocol, unless they have been modified by agreement between Eli Lilly and Company and Covance Early Clinical (EC) Biometrics. A limited amount of information concerning this study (e.g., objectives, study design) is given to help the reader's interpretation. This SAP must be signed off prior to first subject administration for this study. When the SAP and TFL shells are agreed upon and finalized, they will serve as the template for this study's CSR.

This SAP supersedes the statistical considerations identified in the protocol; where considerations are substantially different, they will be so identified. If additional analyses are required to supplement the planned analyses described in this SAP, they may be performed and will be identified in the CSR. Any substantial deviations from this SAP will be agreed upon between Eli Lilly and Company and Covance EC Biometrics and identified in the CSR. Any minor deviations from the TFLs may not be documented in the CSR.

This SAP is written with consideration of the recommendations outlined in the International Council on Harmonisation (ICH) E9 Guideline entitled Guidance for Industry: Statistical Principles for Clinical Trials and the ICH E3 Guideline entitled Guidance for Industry: Structure and Content of Clinical Study Reports.

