### **11. CHANGES FROM THE PROTOCOL SPECIFIED STATISTICAL ANALYSES**

There were no changes from the protocol specified statistical analyses.

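### The SAP drops the ECG listing and summary that the protocol plans, and its section on changes from the protocol declares none

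*SAP*

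**What the plan says.** Protocol 10.3.1.2.4 states: "Other safety parameters that will be assessed include clinical laboratory parameters, vital signs, and ECG parameters". It continues: "The parameters, and changes from baseline (predose) where appropriate, will be listed and summarized using standard descriptive statistics". The protocol synopsis, under Statistical Analysis, gives the general version: "For Parts A and B, safety parameters will be listed and summarized using standard descriptive statistics".

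SAP 9.4.5 consists of one sentence: "ECGs will be performed for safety monitoring purposes only and will not be presented".

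Two other SAP sections govern how such a difference should be handled. SAP 3 says: "This SAP supersedes the statistical considerations identified in the protocol; where considerations are substantially different, they will be so identified". SAP 11 says: "There were no changes from the protocol specified statistical analyses".

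**The concern.** The protocol promises an output for a named safety assessment, the SAP removes it, and the section meant to record departures says that there are none. Safety and tolerability are among the primary objectives in both parts. Protocol 5.1 and SAP 5 both name 12-lead ECGs among the means of exploring them. If the SAP is followed as written, the study report would show no ECG parameter values, no changes from predose, and no abnormalities that fell short of a diagnosis. A reader who relied on SAP 11 would not learn that this output had been planned.

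**Working it through.** **Comparing the texts.** The plan gives no figure to reproduce on this point, so the check is mainly a comparison of sections.

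1. *Is the protocol commitment firm?* Yes. In Protocol 10.3.1.2.4 the qualifier about appropriateness attaches to changes from baseline. The listing and the summary carry no qualifier.
2. *Are the other parameters in that sentence treated the same way?* No. SAP 9.4.3 keeps a summary and listing for clinical chemistry and hematology, and a listing for urinalysis. SAP 9.4.4 keeps a summary, change from Day 1 predose and a listing for vital signs. Only ECG loses all output.
3. *Does the SAP's precedence clause settle it?* Only in part. It decides which document governs, but it also undertakes to identify substantial differences. Removing all output for a named safety parameter is reasonably a substantial difference, and SAP 11 does not identify it.
4. *Do the document versions explain it?* No. SAP 3 says that the SAP was written from the protocol of 13 December 2017 and Amendment (a) of 12 March 2018. For Amendment (b), the amendment summary lists one change, in Section 10.3.7: "An update has been made to introduce an exploratory interim analysis to this study". On that summary, Amendment (b) did not introduce the ECG text.
5. *Does other SAP text restore the listing?* Not clearly. SAP 9.1 promises listings for databased data, but the documents do not say whether ECG values are databased, and 9.4.5 is the more specific rule. SAP 9.4.12 lists only assessments that the section does not otherwise detail, and ECG is detailed there.
6. *Does any ECG information still reach the report?* Yes. Protocol 9.4.3 has each ECG interpreted, its review documented and the recording stored at the site. Clinically significant findings that lead to a diagnosis after the first dose are reported as adverse events through the eCRF. SAP 9.4.1 then lists all adverse events and tabulates the treatment-emergent ones.

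**Counting the recordings.** Inputs are the ECG rows of the two Schedules of Activities and about 36 subjects per part (Protocol 10.1).

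- Part A after screening: Day 1 (0 h), Day 2 (24 h), Day 85/ED, so 3 per subject. 36 × 3 = 108.
- Part B after screening: Day 1 (0 h), Day 2 (0 h), Day 3 (24 h), Day 86/ED, so 4 per subject. 36 × 4 = 144.
- Total after screening: 108 + 144 = 252. Adding one screening ECG per subject gives 252 + 72 = 324.
- Day 1 zero-hour recordings, taken before dosing: 36 + 36 = 72.
- Recordings after the first dose: 252 − 72 = 180 (check: 36 × 2 + 36 × 3 = 72 + 108 = 180).
- Of those 180, the Part B Day 2 zero-hour recordings precede the second injection: 36. The remaining 180 − 36 = 144 follow the last injection.

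**The case against.** The strongest case on the other side is that little of consequence is lost. Table AMAQ.1 gives the safety and pain endpoints as incidence of TEAEs and the SF-MPQ; ECG is neither, and the protocol itself groups it under other safety parameters. Every arm receives LY3074828, so there is no placebo contrast. After the first dose, the scheduled ECGs are single recordings about 24 hours after an injection and at the final visit, whereas Protocol 3.2 reports maximum concentrations 3 days after SC dosing. The same section reports no clinically important drug-related ECG changes in two earlier studies. The SAP also governs, and whether a dropped descriptive table is a substantial difference is a matter of judgement.

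Most of this stands as a limit on importance. It does not make SAP 11's flat statement accurate, and it does not explain why the protocol's commitment no longer applies.

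A reader might go further and infer that the study report would hold no ECG information at all, or that the primary safety conclusions are compromised. The documents support neither reading. Diagnosed, clinically significant findings still reach the adverse event outputs, and no primary estimate or interval uses ECG values. Nor should the 252 recordings be read as 252 post-dose observations, since 72 are baselines.

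**Conclusion.** The inconsistency is real and should be corrected. Protocol 10.3.1.2.4 and SAP 9.4.5 cannot both be followed, and SAP 11 is wrong as to ECGs. The adverse event route covers only findings that lead to a diagnosis, so it does not replace the planned listing and summary. The size is a missing descriptive output, with no effect on the primary PK, TEAE or pain analyses.

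The counts assume 36 subjects per part with complete schedules; dropouts, replacements and unscheduled ECGs would change them. The conclusion also takes the Amendment (b) summary as a complete list of its changes. It does not depend on whether ECG values are databased: if they are, SAP 9.4.5 also conflicts with the listing rule in SAP 9.1; if they are not, the protocol's planned summary cannot be produced without further data entry.

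**What to change.** Replace SAP 9.4.5 with a listing and a descriptive summary of ECG parameters, with changes from Day 1 predose where appropriate. Day 1 predose is the baseline that SAP 9.4.4 already uses for vital signs.

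Present the results by dosing regimen and time point. This layout is a recommendation; Protocol 10.3.1.2.4 does not specify one. In Part B, show the final visit by AI arm or by injection sequence, because by then each subject has received both speeds and the value belongs to neither alone. Day 3 also follows both injections, so showing it by sequence would avoid the same ambiguity.

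If the sponsor prefers to keep the omission, state it with a reason in SAP 11 and align Protocol 10.3.1.2.4.

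The first route costs one listing and one table from ECGs already scheduled. If the values are not databased, it also needs eCRF fields and data entry for up to 252 post-screening recordings, which could be the larger part of the work. The second route costs text changes only. Neither adds a study procedure.

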#### **9.4.6 Hepatic Monitoring**

If a subject experiences elevated alanine aminotransferase (ALT)  $\geq 3 \times$  upper limit of normal (ULN), alkaline phosphatase (ALP)  $\geq 2 \times$  ULN, or elevated total bilirubin (TBL)  $\geq 2 \times$  ULN, liver tests will be performed to confirm the abnormality.

The subjects' liver disease history and associated person liver disease history data will be listed. Any concomitant medication of acetaminophen/paracetamol will be listed. Results from any hepatic monitoring procedures, such as a magnetic resonance elastography (MRE) scan, and a biopsy assessment will be listed, if performed.

Hepatic risk factor assessment data will be listed. Liver related signs and symptoms data will be summarized by treatment and listed. Alcohol and recreational drug use data will also be listed.

All hepatic chemistry, hematology, coagulation, and serology data will be listed. Values outside the reference ranges will be flagged on the individual subject data listings.

#### **9.4.7 Injection Site Assessment**

Injection site assessment data (erythema, induration, categorical pain, pruritus and edema) will be listed and summarized in frequency tables. Whether bleeding occurred will also be listed.

#### **9.4.8 Pain Assessment**

Pain will be assessed by the SF-MPQ and will be quantified using the 100-mm validated VAS where 0 mm represents "no pain" and 100 mm represents "worst possible pain". Assessments will be performed at 0, 15, 30, 60, 120, and 240 minutes post injection; however, the primary endpoint will be the 0-hour assessment.

The data will be summarized by treatment and timepoint and listed for individual subjects. Individual profiles will be presented over time. Furthermore, scatter plots of the 0, 15 and 30 minutes post injection pain scores will be presented by treatment.

In Part A, a linear fixed-effects model will be used to analyze the 0-hour (post-injection) pain VAS score and SF-MPQ total score. The model will include treatment (Reference or Test 1) as a fixed effect. The least squares means and differences in least squares means (between Test 1 and Reference) will be presented along with the corresponding 90% CI. Similar SAS code to the PK statistical analysis will be used.

The distribution of the data will be explored prior to analysis to determine whether data transformation is required. It is possible that the pain scores will be 0 so if the distribution of the data implies that a log-transformation is required then the score may be updated to  $\log(VAS+1)$  to allow for the inclusion of the 0 values in the analysis.

A similar model will be used to analyze the 0-hour (post-injection) pain VAS score and SF-MPQ total score in Part B.

The following comparisons will be performed in Part B:

- Test 2 versus Test 3 (slow versus fast injection for 2-mL AI)
- Test 4 versus Test 5 (slow versus fast injection for 1-mL AI)

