## 5.4. Scientific Rationale for Study Design

Conducting the study in healthy subjects mitigates the potential confounding effects of the disease state and concomitant medications in patients. Healthy subjects are frequently used in the assessment of bioavailability of both small and large molecules.

For Part A, single doses of LY3074828 and the PK sampling time points have been selected to generate PK profiles sufficient to fulfill the study objectives. As the primary endpoints for Part A of this study are PK-related and are not subject to bias, it is not considered necessary for this study to be blinded. Subjects and site staff will be aware of the administration route and treatment.

For Part B, only an evaluation of safety and tolerability of, and pain associated with, the investigational AI administrations is intended. Pharmacokinetic samples are collected only in conjunction with immunogenicity samples to provide concentrations of LY3074828 to aid in the interpretation of ADA data if needed.

For Part A, a parallel-group design was chosen because a crossover design is impractical for compounds that have long half-lives, such as monoclonal antibodies. Additionally, a crossover study design could confound PK data if subjects develop neutralizing ADAs.

For Part B, a crossover design was chosen as PK analysis is not an endpoint and a relatively short time between injections will allow a more accurate comparison of injection-site pain by subjects

Monoclonal antibody therapy has been associated with hypersensitivity reactions, including injection-site reactions. Follow-up details on injection-site reactions will be collected by the investigative site regarding the severity, duration, type, and timing of the start of the event in relation to the start of study drug administration in order to further characterize these events.

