## **7.2. Method of Treatment Assignment**

Subjects will be randomized within 1 study part (Part A or Part B) to 1 of 2 dosing regimen arms ([Table AMAQ.2](#) and [Table AMAQ.3](#)). In addition, the sequence of injections on Days 1 and 2 (fast/slow versus slow/fast) for subjects participating in Part B will be randomized.

Randomization will be performed using a computer-generated randomization schedule.

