### 10.3. Statistical Analyses

Statistical analysis of this study will be the responsibility of Eli Lilly and Company or its designee.

Pharmacokinetic analyses will be conducted on the full analysis set. This set includes all data from all randomized subjects receiving the dose of LY3074828 with evaluable PK data in Part A. Safety analyses will be conducted for all subjects receiving a dose of LY3074828, whether or not they completed all protocol requirements.

Additional exploratory analyses of the data will be conducted as deemed appropriate. Study results may be pooled with the results of other studies for population PK analysis purposes to avoid issues with post-hoc analyses and incomplete disclosures of analyses.

No adjustments for multiple comparisons will be made.

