### Part B

- Tests 2 and 3: 250 mg LY3074828 solution formulation, 1 x 2-mL 125-mg/mL AI slow injection (Test 2; targeting approximately 13-second injection time) and fast injection (Test 3; targeting approximately 5-second injection time) using an investigational 2-mL AI
- Tests 4 and 5: 125 mg LY3074828 solution formulation, 1 x 1-mL 125 mg/mL AI slow injection (Test 4; targeting approximately 7-second injection time) and fast injection (Test 5; targeting approximately 4.5-second injection time) using an investigational 1-mL AI

For Part A, subjects will report to the clinical research unit (CRU) on Day -1 and will remain at the CRU until the scheduled procedures have been completed on Day 2. After randomization to either a 2 x 1-mL or a 1 x 2-mL 125-mg/mL PFS dose regimen, study drug will be administered by investigative site staff by SC injection in the abdomen in the morning of Day 1 after an overnight fast.

For Part B, subjects will report to the CRU on Day -1 and will remain at the CRU until the scheduled procedures have been completed on Day 3. Subjects will be randomized to receive, on Days 1 and 2, either a 1 x 1-mL or a 1 x 2-mL 125-mg/mL AI dose regimen. The allocated AI dose regimen will be self-administered by slow and fast SC injection(s) on consecutive days (sequence randomized) in the abdomen after an overnight fast.

Safety and tolerability will be explored by clinical laboratory tests, vital sign measurements, 12-lead electrocardiograms (ECGs), recording of adverse events (AEs) and product complaints, physical examinations/medical assessments, immunogenicity, and injection-site assessments. Pain assessments will be made using the Short Form McGill Pain Questionnaire (SF-MPQ), which includes a subject-assessed injection-site pain visual analog scale (VAS).

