## **8. DEFINITION OF ANALYSIS POPULATIONS**

The “Safety” population will consist of all subjects who received a dose of LY3074828 whether or not they completed all protocol requirements.

The “Pharmacokinetic” population will consist of all randomized subjects who received at least one dose of LY3074828 and have evaluable PK data in Part A.

All protocol deviations that occur during the study will be considered for their severity/impact and will be taken into consideration when subjects are assigned to analysis populations.

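### Part B is a slow/fast crossover, but its 0-hour pain model is defined only by reference to Part A's treatment-only model, which read literally discards the pairing

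*SAP*

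**What the plan says.** SAP 9.4.8 sets out one pain model in full, the linear fixed-effects model for Part A: "The model will include treatment (Reference or Test 1) as a fixed effect". It points to SAS code similar to the PK code in SAP 9.3.2. That code has arm as its only model term and no RANDOM or REPEATED statement.

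For Part B the SAP says only this: "A similar model will be used to analyze the 0-hour (post-injection) pain VAS score and SF-MPQ total score in Part B". Protocol 10.3.1.2.1 and the statistical section of the synopsis use the same sentence. The comparisons named for Part B are Test 2 versus Test 3 (2-mL autoinjector) and Test 4 versus Test 5 (1-mL autoinjector), each slow versus fast. The 0-hour assessment is the primary pain endpoint.

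The design differs from Part A. Protocol 5.4 states: "For Part B, a crossover design was chosen as PK analysis is not an endpoint". Its reason is that "a relatively short time between injections will allow a more accurate comparison of injection-site pain by subjects". Protocol 7.2 adds that "the sequence of injections on Days 1 and 2 (fast/slow versus slow/fast) for subjects participating in Part B will be randomized".

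Subjects with only one injection are not excluded. SAP 8 defines the Safety population as "all subjects who received a dose of LY3074828 whether or not they completed all protocol requirements", and Protocol 10.3 says the same of the safety analyses.

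**The concern.** Both named comparisons are within subject. A model whose only term is treatment assigns all between-subject variation in pain scoring to the residual and treats a subject's two scores as unrelated. If people who score high on one day tend to score high on the next, the standard error of the slow-fast difference is overstated.

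These are the only pain comparisons named for Part B, and pain is part of its primary objective. Over-wide intervals would make a real effect of injection speed harder to see and would give away the advantage for which the crossover was chosen.

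Two smaller matters follow from the same gap. Without a period term, an unequal split between the two sequences lets part of any Day 1/Day 2 effect into the slow-fast difference. And the weight given to a subject with a single score is undefined. Such subjects can arise: under Protocol 8.1.1, a Part B subject found before the second dose to have been enrolled in error does not receive it.

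**Working it through.** The documents give no precision or power figure for the Part B pain comparisons, so there is none to reproduce. (The 0.28 in Protocol 10.1 and SAP 7 concerns the Part A PK ratios.)

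**Inputs**
- Pairs per device: 18 randomised, 16 intended to complete (Protocol 10.1, SAP 7). The main calculation uses n = 16.
- Interval: two-sided 90% (stated for Part A in SAP 9.4.8 and carried over by the reference to a similar model).
- Pain SD s and correlation ρ between a subject's two scores: not given. Results are in SD units, for ρ = 0, 0.3, 0.5 and 0.7.
- Assumed: complete pairs, 8 per sequence, normal scores, equal SDs, a separate model for each device.

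**Formulas**
- True variance of the slow-fast mean difference: 2s²(1−ρ)/n. The treatment-only model uses 2s²/n.
- Treatment-only half-width: t(0.95, 2n−2) × s√(2/n) = 1.697 × √(2/16) = 0.600 SD.
- Crossover half-width (subject, period and speed in the model): t(0.95, n−2) × s√(2(1−ρ)/n) = 1.761 × √(2(1−ρ)/16) SD.
- Ratio: (1.697/1.761)/√(1−ρ) = 0.964/√(1−ρ).

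| ρ | Treatment-only (SD) | Crossover (SD) | Ratio | Simulated coverage, treatment-only |
|---|---|---|---|---|
| 0 | 0.600 | 0.623 | 0.96 | 0.899 |
| 0.3 | 0.600 | 0.521 | 1.15 | 0.948 |
| 0.5 | 0.600 | 0.440 | 1.36 | 0.975 |
| 0.7 | 0.600 | 0.341 | 1.76 | 0.994 |

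Coverage comes from 40,000 simulated trials. The crossover model stayed at 0.898 to 0.900, and the two point estimates were identical. A separate run of 200,000 trials agreed to within 0.003. At ρ = −0.3 it gave the treatment-only interval a coverage of 0.853, so with negative correlation that interval is too narrow.

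**Break-even.** The widths are equal when ρ = 1 − (1.697/1.761)² = 0.071. With 18 pairs it is 1 − (1.691/1.746)² = 0.062. Below this, the crossover model's loss of degrees of freedom outweighs its gain. Coverage above 90% starts earlier, just above ρ = 0.

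**In pairs.** A crossover model reaches a half-width of 0.600 SD or less with:
- 13 pairs at ρ = 0.3: 1.796 × √(1.4/13) = 0.589
- 10 pairs at ρ = 0.5: 1.860 × √(1.0/10) = 0.588
- 7 pairs at ρ = 0.7: 2.015 × √(0.6/7) = 0.590

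**Skewed scores.** Simulated scores with a long right tail and 14% zeros, analysed as log(VAS+1), gave ratios of 0.97, 1.16, 1.36 and 1.74 at observed correlations of 0, 0.29, 0.49 and 0.69. On the raw scale the ratios were 0.97, 1.10, 1.25 and 1.55 at 0, 0.22, 0.39 and 0.60.

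**Unequal sequences (assumed splits).** If 9 of 16 subjects inject slowly first, the treatment-only difference takes in (9−7)/16 = 0.125 of any day effect. At 10/6 it takes in (10−6)/16 = 0.25. With a period term it takes in none.

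**The case against.** **'Similar' need not mean identical.** The Part A term is Reference or Test 1, and neither exists in Part B, so the model has to be adapted. PROC MIXED can take a subject effect, the pointer to the PK code stands in the Part A paragraph, and the TFL shells mentioned in SAP 3 were not available to check. This is fair: the documents show that the model is under-specified, not that the wrong one will be run. But nothing in either document leads a programmer to the paired model. SAP 5 calls the whole study parallel-treatment, and SAP 11 records no changes. A plan that permits both models leaves open which interval is reported.

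**The figures depend on choices the documents do not make.** A single treatment-only model across Tests 2 to 5 would have 60 degrees of freedom at 16 per device (t = 1.671). Against the same crossover comparator, break-even moves to 1 − (1.671/1.761)² = 0.10, and the ratios become 0.95, 1.13, 1.34 and 1.73. The 0-hour scores are taken on Days 1 and 2 while subjects are resident, so 18 pairs may be available. The ratio is then (1.691/1.746)/√(1−ρ), or 0.97, 1.16, 1.37 and 1.77. Neither changes the conclusion.

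**The consequence is limited.** With complete pairs and equal sequences the estimate is unchanged. With positive correlation the error is conservative. No margin or decision rule is attached, and SAP 9.4.13 says that no inferential safety analysis is planned. All of this keeps the point below the most serious level. SAP 9.4.13 does not, however, cancel the comparisons that SAP 9.4.8 plans; the two sections conflict, which adds to the ambiguity.

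**Protocol 5.4 does not mention correlation.** It credits the short interval between injections. That a gain from pairing is meant is an inference, though a natural one for a crossover.

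**Conclusion.** The concern holds and should be fixed. The only pain model written out does not fit the Part B design. Followed literally with positively correlated scores, it gives intervals that are too wide: about 15%, 36% and 76% wider than a crossover analysis at correlations of 0.3, 0.5 and 0.7, with 16 complete pairs per device, equal SDs and balanced sequences. At zero correlation the literal interval is about 4% narrower and keeps its nominal coverage, so nothing is lost there.

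The omission is certain from the text. The size of the loss is illustrative, because it depends on a correlation that the documents do not give.

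**What to change.** In SAP 9.4.8, replace the reference to a similar model with an explicit Part B model, fitted separately for the 2-mL and the 1-mL autoinjector:

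- Fixed effects for injection speed (slow, fast) and period (Day 1, Day 2).
- Subject accounted for, either as a random effect within sequence with a sequence term, or as a fixed effect. With complete pairs both give the same slow-fast estimate, so either is acceptable, but the SAP should name one.
- The slow-fast difference in least squares means, with its 90% CI.
- A rule for subjects with one injection. Under a random subject effect their score stays in the model; under a fixed one it carries no weight in the comparison.

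Make the same replacement in Protocol 10.3.1.2.1 and the synopsis. SAP 3 says that the SAP supersedes the protocol's statistical considerations, so the SAP edit has effect by itself, and the protocol text can follow at its next amendment. Reconcile SAP 9.4.13 with 9.4.8 at the same time.

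The cost is one sentence in three places and a few lines of code. Subject, day and sequence are already part of the design, so no new data and no more subjects are needed. The change should be made before Part B pain data are examined by injection speed: Protocol 10.3.6 allows data to be analysed while the trial is ongoing, and Protocol 10.3.7 plans an exploratory interim analysis.
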